January 17, 2024

Protocol Title: Hoarding Disorder Treatment With Virtual Reality

NCT Number: NCT03828461

Study Protocol/Method

Procedure overview

Participants diagnosed with HD participated in study interventions for 16 weeks, including 16 weeks of remote BIT group sessions and 8 weeks of in-person individual VR-based sessions (the two session types overlapped during weeks 7–14 of BIT). VR environments were individualized to look like each participant's cluttered room. Primary outcome assessments were collected at Baseline (Week 0), immediately before starting VR sessions (Week 6), and at Close Out (Week 17). Participants completed the SSQ at the end of every session.

Virtual reality treatment protocol

Beginning seven weeks into the BIT group sessions, eight weekly 1-h individual VR sessions were administered (one for orientation; seven using the VR). Session content was consistent with protocols for in-home decluttering visits (Linkovski et al., 2018). VR sessions were administered by doctoral trainee clinicians trained in the treatment protocol and VR equipment. Sessions were designed to augment sorting and discarding skills learned in the BIT group; they are described in more detail below. In the first session, participants received psychoeducation on the VR approach, and in Session 2, they familiarized themselves with the virtual home. In Sessions 2 and 3, the focus was on practicing cognitive skills with the virtual objects. This included identifying core beliefs about objects (“If you discarded this magazine, why would it be so upsetting?”) and thinking through decision-making skills (“How many mugs would be ‘enough?’”), while holding the virtual object in question (a magazine, a mug) and at times subsequently placing it into the virtual trash, recycling, or donation bins. In Sessions 4 through 8, focus was on desensitizing to discarding in the virtual home. Participants created a hierarchy of how distressing it would feel to discard each virtual object, then started discarding items lower on the hierarchy and worked their way up. In virtual discarding, they placed objects into bins (trash, recycle, donate; there was no “keep” bin although this is sometimes used in real-life discarding practice). An animated trash truck came to pick up the items placed in the trash. Participants were encouraged to lean into the psychological immersion of the process and the worry thoughts associated with discarding. During virtual discarding, they regularly rated their subjective distress on a scale of 0–10. As homework, they were assigned to actually discard one of the items that they had virtually discarded in session (or a similar item). In the final (8th) session, in addition to the VR activities, a relapse prevention plan was also made.

BIT Peer support group treatment protocol

The BIT group met online once per week for 16 weeks and followed the structured format detailed in the Buried in Treasures workbook (Tolin et al., 2013) and the BIT facilitator's guide (Shuer and Frost, 2011). Each 2-h group session was led by two study staff group facilitators (KV, TA), one of whom was a doctoral trainee clinician. The content began with psychoeducation about HD and non-acquiring skills,

and then provided educational content regarding skills for discarding possessions (e.g., behavioral experiments where one discards an item and then tracks how distressing it feels).

Statistical Analysis Plan

The relatively small sample size limits inference-based statistics such as mixed effects models (MEMs); thus, primary analyses will be descriptive statistics. It is generally recommended that analysis of small samples, such as the present study, be descriptive (Grimes and Schulz, 2002; Lancaster et al., 2004). The goal is for preliminary data to support the potential effectiveness of this approach, which can then be examined in a larger study. For primary outcome measures, we calculated the reliable change index (RCI; Jacobson and Truax, 1991), a statistical approach for measuring individual change in self-report scores; RCIs greater than 1.96 indicate reliable change, likely attributable to treatment rather than measurement error. To be thorough, we also note clinically significant change on the SIR using a stringent standardized criterion for this questionnaire (Norberg et al., 2021).

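### Does the SSQ need a planned comparison with the no-VR first session, so that VR-induced symptoms can be told from existing ones?

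*Combined protocol and SAP*

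**What the plan says.** The SSQ appears once, in the Procedure overview: "Participants completed the SSQ at the end of every session". The abbreviation is not expanded, and no reading before a session is described. The same section sets the main assessment times separately ("Primary outcome assessments were collected at Baseline (Week 0), immediately before starting VR sessions (Week 6), and at Close Out (Week 17") and does not list the SSQ there. Just before that it describes two kinds of session, "including 16 weeks of remote BIT group sessions and 8 weeks of in-person individual VR-based sessions", so the scope of the SSQ sentence is open.

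The section on the virtual reality treatment protocol says that "eight weekly 1-h individual VR sessions were administered (one for orientation; seven using the VR". It adds: "In the first session, participants received psychoeducation on the VR approach, and in Session 2, they familiarized themselves with the virtual home". The first individual session is therefore without VR exposure, and Sessions 2 to 8 are the exposed ones.

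The Statistical Analysis Plan says of the small sample, "thus, primary analyses will be descriptive statistics". It continues, "For primary outcome measures, we calculated the reliable change index", and adds a clinical-significance criterion for the SIR. The SSQ is not among the measures named.

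**The concern.** Take the SSQ to be a simulator-sickness questionnaire, as its use at every session of a VR study suggests. A score at the end of a session is then the person's background level plus whatever VR added, and one reading cannot split the two. With no analysis written down, two poor summaries are possible. Raw scores could be read as VR effects, which charges all background symptoms to VR. All sessions could be averaged, which mixes unexposed readings with exposed ones and hides part of a real rise. Session 1 looks like a within-person reference that costs nothing to use, so leaving it unused seems wasteful. At stake would be what the study can say about how well the VR sessions were tolerated, which matters to a pilot meant to support a larger study.

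**Working it through.** **Inputs.** Individual sessions: 8, of which 1 is orientation and 7 use VR (virtual reality treatment protocol). Overlap with the group sessions: weeks 7 to 14; group sessions: 16 (Procedure overview). The documents give no sample size, SSQ mean or SSQ variability, so results below are in units of s, an assumed SD of a person's session-to-session error, taken as independent between sessions.

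**1. Session count.** 1 + 7 = 8, and 14 − 7 + 1 = 8 weeks. The two descriptions agree.

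**2. What pooling would do.** Let B be a person's background level and V the VR-induced rise, with no VR effect in Session 1.

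- Mean over Sessions 2–8: B + V.
- Mean over all 8 individual sessions: B + 7V/8. The rise is diluted by 1 − 7/8 = 12.5%. The raw mean falls by the fraction (V/8)/(B + V), which is below 12.5% whenever B > 0.
- Mean over all 24 sessions, if the group sessions also count (16 + 8): B + 7V/24. About 29% of the rise is kept and 71% lost.

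The arithmetic is right, but no section plans any of these averages.

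**3. What a by-session table would do.** Session 1 shows B, and each of Sessions 2–8 shows B + V. Nothing is diluted, and a reader can subtract one from the other without a planned change score.

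**4. How precise the Session 1 contrast is.** For one person, the mean of Sessions 2–8 minus a reference built from n unexposed readings has variance s²(1/7 + 1/n).

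| Reference | Variance / s² | SE / s | Share of variance from reference |
|---|---|---|---|
| Session 1 only (n = 1) | 1/7 + 1 = 1.143 | 1.07 | 1/1.143 = 87.5% |
| Session 1 plus the 6 group sessions before VR (n = 7) | 1/7 + 1/7 = 0.286 | 0.53 | 50% |

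The second row applies only if the SSQ was also given at group sessions. For comparison, readings before and after each of the 7 VR sessions would give SE = s√(2(1 − f)/7), where f is the share of the variance common to both readings on the same day: 0.53 s at f = 0 and 0.27 s at f = 0.75. Those pre-session readings are not in the schedule.

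**5. Worst change from Session 1.** With normal errors and V = 0, the largest of 7 independent errors has expectation of about 1.35 s, and the reference error has expectation 0. The expected worst change is therefore about +1.35 s with no VR effect.

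**The case for a change.** The strongest case for acting is that a few words would settle it at almost no cost. The SSQ is scheduled at every session, it is the natural tolerability measure in a VR study, and the SAP is silent on it. Silence leaves the choice of summary open until the data are seen. The unclear scope widens the room for error, since the dilution under careless pooling runs from 12.5% to 71% depending on which sessions are covered.

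Part of this stands. The abbreviation is undefined, the scope is unstated, and no summary is named. A report should say what the SSQ is and which sessions it covers, and should show the orientation session apart from the VR sessions. Any analyst who knows that one session had no VR would do the last of these unprompted.

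The rest does not carry. No safety or tolerability objective is stated; the SAP's declared goal is preliminary evidence of potential effectiveness. The claim that Session 1 is the trial's only reading without VR fails if group sessions are covered, and writing into the plan that only individual sessions count could misdescribe what was done. A Session 1 reference also removes only stable background. It is taken a week or more before the exposed sessions and cannot account for symptoms a person brings to a later visit.

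**Conclusion.** The concern does not call for a change. The facts behind it are right: readings come only at the end of sessions, Session 1 has no VR, and the SAP names no SSQ analysis. But this is an unwritten secondary summary in a descriptive study, not a rule that gives a wrong answer. The 12.5% dilution and the full attribution of background symptoms to VR belong to analyses that the plan does not propose. If the SSQ sentence is taken at its word, the unexposed reading is already collected, and a table by session uses it.

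The suggested replacement is not clearly better. It depends heavily on one reading, and its worst-change column would overstate VR symptoms, the very fault it is meant to cure. These two results assume independent session errors, and the second also assumes normality; the documents give no SSQ data to test either. The whole point further assumes that the SSQ measures VR-induced symptoms. Whatever is done with it, the reliable change results and the SIR criterion are unaffected.

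### An RCI above 1.96 is read as change likely due to treatment, but the index says nothing about cause and the design has no comparison group or untreated period

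*Combined protocol and SAP*

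**What the plan says.** The Statistical Analysis Plan makes descriptive statistics primary because the sample is small. For the primary outcome measures it calculates the RCI, which it describes as "a statistical approach for measuring individual change in self-report scores", and it gives the reading rule: "RCIs greater than 1.96 indicate reliable change, likely attributable to treatment rather than measurement error". It also notes clinically significant change on one questionnaire, the SIR. The purpose is put modestly: "The goal is for preliminary data to support the potential effectiveness of this approach", with a larger study to follow.

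The Procedure overview describes a single course for all participants: 16 weeks of BIT group sessions and 8 weeks of individual VR sessions, where "the two session types overlapped during weeks 7–14 of BIT". Primary outcomes are assessed at Week 0, at Week 6 just before VR starts, and at Week 17. No comparison group, waiting list or untreated run-in is described. The VR section adds that "Sessions were designed to augment sorting and discarding skills learned in the BIT group", so the two components are linked in content as well as in time.

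**The concern.** The reading rule offers two explanations for a large change, treatment or measurement error, and treats evidence against the second as evidence for the first. Real change can have other sources: the natural course of the disorder, expectancy, and the effect of completing the same self-report scales repeatedly. The RCI flags change from any of these exactly as it flags a treatment effect. Regression to the mean is a separate matter. It comes from unreliability and is not real change, but it also raises the flag rate when people enter with high scores.

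A comparison group or an untreated period could have shown how much change occurs without treatment. The documents describe neither. Followed as written, the clause credits treatment with change that the design cannot attribute to BIT, to VR or to the two together.

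**Working it through.** **The cut-off.** The two-sided 5% normal quantile is 1.95996, which rounds to the SAP's 1.96. The tail beyond 1.96 is 0.0250 in each direction. The null behind this figure is no true change, with score differences due only to measurement error. The cause of change does not enter it.

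**The schedule**, from the Procedure overview:

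| Interval | BIT weeks | of which with VR | BIT alone |
|---|---|---|---|
| Baseline to Week 6 | 1–6 (6 weeks) | 0 | 6 |
| Week 6 to Week 17 | 7–16 (10 weeks) | 8 (weeks 7–14) | 2 |
| Total | 16 | 8 | 8 |

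BIT-free weeks: 16 − 16 = 0. VR-only weeks: 8 − 8 = 0. The first interval is free of VR but not of treatment, so it cannot stand in for an untreated baseline. In the second interval BIT continues alongside VR.

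**How non-treatment change affects the flag rate.** The documents give no reliability, SD, entry score or expected untreated change, so everything from here is illustration. I use the usual form, scored so that improvement is positive:

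RCI = change / (SD × √(2(1 − r))), with r the reliability.

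I assume normal errors and r from 0.80 to 0.90.

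- √(2(1 − r)) is 0.632 at r = 0.80 and 0.447 at r = 0.90. RCI = 1.96 is then a change of 1.96 × 0.632 = 1.24 SD, or 1.96 × 0.447 = 0.88 SD.
- With zero treatment effect and a uniform improvement of d SD from any other cause, the share flagged is P(Z > 1.96 − d/√(2(1 − r))):

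| d (SD) | r = 0.80 | r = 0.90 |
|---|---|---|
| 0 | 2.5% | 2.5% |
| 0.25 | P(Z > 1.96 − 0.395) = 5.9% | P(Z > 1.96 − 0.559) = 8.1% |
| 0.50 | P(Z > 1.96 − 0.791) = 12.1% | P(Z > 1.96 − 1.118) = 20.0% |

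- The shift that doubles 2.5% to 5% is (1.96 − 1.645) × √(2(1 − r)) = 0.20 SD at r = 0.80 and 0.14 SD at r = 0.90.

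**Regression to the mean, taken separately, with no true change.** For a person entering z SD above the reference mean, the RCI has mean z(1 − r)/√(2(1 − r)) and SD √((1 + r)/2).

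| Entry z | r = 0.80 | r = 0.90 |
|---|---|---|
| 1 | P(Z > (1.96 − 0.316)/0.949) = 4.2% | P(Z > (1.96 − 0.224)/0.975) = 3.7% |
| 2 | P(Z > (1.96 − 0.632)/0.949) = 8.1% | P(Z > (1.96 − 0.447)/0.975) = 6.0% |

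Whether this applies here is unknown, because no entry scores are given.

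**The SIR criterion.** Clinically significant change also classifies a person's change. It supplies no comparison, so it does not help with cause.

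**The case against.** The strongest reply is that this is one hedged clause in a modest plan. It says likely, it contrasts treatment with measurement error, and it can be read as loose shorthand for real change versus noise. The same paragraph declines formal inference and leaves effectiveness to a larger study. The hedge and the framing do limit the harm. They do not repair the inference: making error unlikely does not make treatment likely, and a descriptive plan should not carry a causal reading of its primary measures.

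A second reply is that the SAP never claims a VR effect, and that Week 6 allows a within-person comparison of BIT alone with BIT plus VR. Both are true. The SAP does not say whether treatment means BIT, VR or both, nor which interval the RCI covers. But the Week 6 comparison sets 6 elapsed weeks against 11, and BIT continues through the VR weeks. It therefore cannot isolate VR, and it cannot show that the package as a whole caused change.

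A third reply is that the percentages rest on assumed values. That is also true. They show how an RCI behaves and do not estimate anything in this trial. The point does not depend on them.

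Finally, the documents are largely in the past tense, so the work may already be finished. What can still change is the wording of the plan and the interpretation in any report, which is not available here.

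**Conclusion.** The concern holds. The 1.96 cut-off is correct for its purpose, but the conclusion drawn from it is not supported. Two facts from the documents carry the point: the RCI tests only against measurement error, and the schedule has no comparison group and no untreated week among the 16. The size of any misattribution in this trial cannot be calculated from the documents. Under the assumed reliabilities, modest change from other causes would raise the flag rate from 2.5% to between 5.9% and 20.0%. The consequence is over-interpretation of the primary outcome measures. The cut-off, the calculations and the counts of participants flagged are unaffected. It should be corrected.

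**What to change.** Replace the clause in the Statistical Analysis Plan with:

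> *An RCI beyond 1.96 indicates change unlikely to be due to measurement error alone; because no comparison group was included, it does not show that treatment (BIT or VR) caused the change.*

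Use the same reading in the results and conclusions. Describe the Week 6 to Week 17 change as change during BIT plus VR, not as an effect of VR.

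The cost is wording only, in the SAP and the report. No new data or analysis is needed. The claim becomes slightly less favourable.

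### Does the reliable change rule, which states no sign and no category for worsening, let deterioration go unreported?

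*Combined protocol and SAP*

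**What the plan says.** The Statistical Analysis Plan is one paragraph. Because the sample is small it sets inferential models aside: "thus, primary analyses will be descriptive statistics". On individual change it says: "For primary outcome measures, we calculated the reliable change index (RCI; Jacobson and Truax, 1991), a statistical approach for measuring individual change in self-report scores". The rule for reading the index follows at once: "RCIs greater than 1.96 indicate reliable change, likely attributable to treatment rather than measurement error". One further individual criterion applies to one questionnaire and is defined by citation: "we also note clinically significant change on the SIR using a stringent standardized criterion for this questionnaire". The purpose is modest: "The goal is for preliminary data to support the potential effectiveness of this approach", with a larger study to follow.

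The Procedure overview places the primary assessments at Weeks 0, 6 and 17. Nowhere do the documents give the order of subtraction, the direction of scoring, a lower limit of -1.96 or a label for reliable deterioration. They also do not say how the index will be tabulated, or which pair of visits it uses.

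**The concern.** The rule can be read in two ways, and neither requires worsened participants to be counted separately.

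- **Signed, improvement positive.** A participant with an index of -3 does not exceed 1.96 and is grouped with those who showed no reliable change.
- **Absolute value.** The same participant exceeds the cut-off and joins the improvers under one label. The sentence goes on to call such change probably due to treatment.

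No comparator is described and the analysis is descriptive, so the number of participants with reliable change could carry much of the argument for a larger study. If that number ignored worsening, or included it, net benefit would look larger than it was. The other repeated measures do not fill the gap: neither the SSQ after each session nor the 0-10 distress rating during virtual discarding is described as a primary outcome.

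**Working it through.** **1. The plan's own figure.** The only number is the cut-off. The normal quantile for a two-sided 5% level is 1.95996, which rounds to 1.96; a one-sided 5% level would give 1.645. With no true change, P(RCI > 1.96) = 0.025 and P(RCI < -1.96) = 0.025, together 0.05. The SAP states no level, so 5% two-sided is inferred. The cut-off is sound, and separating the two tails would not alter it.

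**2. How often reliable worsening would occur.** The documents give no sample size, reliability or expected effect, so every input here is an assumption. Let r be the reliability, m the mean improvement and t the SD of true change, with m and t in baseline SD units and improvement positive. The standard error of a difference is s = √(2(1 − r)), and observed change is taken as N(m, s² + t²). Then

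- P(reliably worse) = Φ((−1.96s − m)/√(s² + t²))
- P(reliably better) = 1 − Φ((1.96s − m)/√(s² + t²))

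For r = 0.9, s = √0.2 = 0.447 and 1.96s = 0.877. For t = 0.5, √(0.2 + 0.25) = 0.671. With m = 0.5, P(worse) = Φ(−1.377/0.671) = Φ(−2.05) = 0.020.

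| r | m | t | Reliably worse |
|---|---|---|---|
| 0.9 | 0.5 | 0 | 0.1% |
| 0.9 | 0.5 | 0.5 | 2.0% |
| 0.8 | 0.5 | 0.5 | 1.5% |
| 0.95 | 0.5 | 0.5 | 2.9% |
| 0.9 | 0.5 | 0.8 | 6.7% |
| 0.9 | 1.0 | 0.5 | 0.3% |
| 0.9 | 0 | 0 | 2.5% |
| 0.9 | 0 | 0.5 | 9.6% |

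**3. In participants.** Take n = 10 as an assumption, with participants independent. At 2.0% the expected number is 0.2, and the chance that nobody is flagged as worse on a given measure and interval is (1 − 0.0201)^10 = 0.82. At 0.3% (0.0026 unrounded) that chance is about 0.97. At 9.6% the expected number is about 1, and the chance of at least one is 1 − (1 − 0.0957)^10 = 0.63.

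**4. If the two tails were pooled.** At r = 0.9, m = 0.5, t = 0.5, the flagged share is 28.7% + 2.0% = 30.7%, of which 2.0/30.7 = 6.5% have worsened. At m = 0, t = 0.5, it is 9.6% + 9.6% = 19.1% (from unrounded values), and half have worsened.

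**5. What the text commits the analyst to.** The index is a signed difference divided by its standard error. It cannot be computed without choosing an order of subtraction, and it cannot be read as better or worse without knowing the direction of the scale. Whoever computes it therefore already holds the information that the sentence omits. The SAP prescribes neither a count that discards negative values nor one that ignores their sign. When the rule contrasts treatment with measurement error, it separates change from noise; it does not say that all such change is benefit.

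**The case for a change.** The strongest case for acting is that the gap is real on either reading and closing it would be cheap. A convention in the cited source cannot be credited to the plan, because the plan does not state it. The treatment asks participants to face distress over discarding and to discard real items as homework, so whether anyone became reliably worse is a fair question. The gap would also matter most where the treatment works least: with no mean improvement, an n of 10 would give a 63% chance of at least one reliably worse participant per measure.

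Part of this stands. The plan does not require worsening to be labelled, and a report that did label it would be clearer. The step from there to overstated benefit does not stand. It needs a form of reporting that the SAP does not prescribe, and an analyst who disregards the sign of a difference already computed. Signed values or individual scores, which suit a small sample, would show any deterioration. The larger figures mostly need zero mean improvement, and then any descriptive summary that includes average change would show no benefit alongside the counts. The 6.7% figure is the exception, and it needs an SD of true change of 0.8, larger than the assumed mean improvement.

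Timing also limits what an edit could do. The document is dated January 2024 and describes the assessments and the index in the past tense, so new wording would in effect be a request about reporting.

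**Conclusion.** The observation is accurate, but it concerns missing detail that an analyst fills sensibly. The cut-off is right and no stated number is wrong. Nothing in the SAP directs that worsening be dropped or merged with improvement. Under the middle assumptions (reliability 0.9, mean improvement 0.5 SD, SD of true change 0.5 SD), about 2% of participants would be reliably worse, or 0.2 of a participant at an assumed n of 10. Under the least favourable case on the 0 to 0.5 SD grid the share is 9.6%, about one participant, and there average change would also show no benefit. These sizes rest wholly on assumed inputs and on normally distributed change. The conclusion rests mainly on the text: the index is signed by construction, the analysis is descriptive and the aim is preliminary. No change to the plan is needed.
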